9.7 DATA ANALYSIS

The study population consists of COPD patients that have received LAMA and ICS/LABA treatment. The study consists of three stages: a) identification and extraction of LAMA-exposed and ICS/LABA-

exposed cohort, b) matching between LAMA-exposed and ICS/LABA-exposed and c) descriptive analysis of cohorts and analysis of outcomes.

Detailed methodology for summary and statistical analyses of data generated in this study will be documented in an SAP. The SAP may modify the plans outlined in the protocol; any major modifications of primary endpoint definitions or their analyses would be reflected in a protocol amendment.

For the purpose of this study, analyses will be conducted using SAS statistical software and R. To address the imbalance of potential confounders between LAMA ICS/LABA groups, we matched treatment groups using propensity scores estimated as by multiple logistic regression analysis *based on* as age, sex, socioeconomics status, *Charlson Comorbidity Index*, and asthma, history of COPD exacerbation. Demographics and clinical characteristics will be tabulated. Frequencies and percentages will be presented for categorical variables. For continuous variables, means, standard deviations, and ranges, or medians and inter-quartile ranges, will be reported as appropriate. We used a standardised difference to compare baseline characteristics between COPD patients who were treated with LAMA and those treated with ICS/LABA. The matched Cox proportional hazards regression analyses will be used to estimate hazard ratios (HRs) HRs and 95% confidence intervals (95% CIs) for all outcomes. For (possibly) repeating events (such as *exacerbation event*) *additionally* a Poisson regression model will be fitted for the number of events (taking into account the matching). The cox and Poisson models will be adjusted for unbalanced PS-variables at baseline. Mortality was estimated by the Kaplan-Meier method, and results were compared between groups using the log-rank test.

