9.7.1.1 Propensity score methodology

The propensity score will model the likelihood among COPD patients of receiving LAMA and ICS/LABA. The model for the propensity score will to the extent possible include the following elements:

- 1) Age and sex
- 2) Socioeconomic status (e.g. income, educational level, single living)
- 3) History of COPD exacerbation
- 4) Charlson Comorbidity Index
- 5) History of asthma

A logistic regression analysis will be performed on the identified COPD patients where treatment with LAMA and ICS/LABA groups is the dependent, dichotomous variable and the independent variables are listed above (age, sex and history of COPD exacerbation et al.). Based on this analysis, the propensity score is calculated for each patient. For subgroup analyses, PS matching and evaluation of its success, as presented below, will be re-done as covariate balance is not automatically maintained in sub-cohorts.

Smoking may be an important confounder in COPD but smoking status is usually not available in the databases at all. If smoking status is confirmed to be available, the data will be analysed with and without smoking status included in the model and the magnitude of the confounding effect assessed (sensitivity analysis).

PS matching will be done in a 1:1 ratio using the nearest-neighbor algorithm, using calipers of width equal to 0.2 of the standard deviation of the logit of the PS (matches of the main exposure sub-cohort and the comparator sub-cohort are formed if the caliper width is not exceeded for the logit of PS). For LAMA-exposed patient to ICS/LABA-exposed patients will be selected within the same matching interval of the propensity score. The distribution of propensity scores will be examined between LAMA-exposed and eligible ICS/LABA-exposed. In the matching procedure, matched comparator sub-cohort patients (ICS/LABA) will be removed from the pool of eligible patients among the comparator sub-cohort so that a matched patient is no longer available for consideration as a potential match for another exposed patient.

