Evaluation of the success of the matching procedure will be based on a standardized difference (detailed below) of a covariate that is less than 0.1 between treatment groups. A standardized difference of a covariate of less than 0.1 between treatment groups in this study indicates a negligible difference in the mean or prevalence of the covariate. If larger standardized differences than 0.1 for some covariates exist after matching, they will be used in post-matching adjustments (i.e. PS-variables with standardized difference >0.1 will be adjusted for in the analyses). Further adjustments can also be made as appropriate in additional models. Based on differences identified through exploratory analysis of baseline variables, we matched individual patients from each cohort (1:1) to ensure comparison of similar patients.

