9.12 BIAS

This study will include users of LAMA and ICS/LABA. Immortal time bias will be minimal, as the follow-up will begin at the initiation of drug use. Adherence to drug use will be unknown.

Comparing the outcomes between users of LAMA and ICS/LABA will decrease confounding by indication, as the comparison group will have a similar indication to drug use than the patients in the LAMA-exposed cohorts.

The compared sub-cohorts will be matched on the basis of PS. The PS will be computed on the basis of a wide range of covariates related to sociodemographic characteristics, history of exacerbation, other comorbidities, and prior/concomitant use of other drugs. The PS matching will decrease the systematic differences between the sub-cohorts and, thus, decrease confounding.

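### Apart from asthma and exacerbation history, the propensity score relies on the Charlson index for comorbidity, with no committed balance check on its component diseases, while section 9.12 describes a wider score

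*Combined protocol and SAP*

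**What the plan says.** Section 9.7.1.1 opens its covariate list with "The model for the propensity score will to the extent possible include the following elements" and gives five items. Three are age and sex, socioeconomic status, and history of COPD exacerbation. The other two are the "Charlson Comorbidity Index" and "5) History of asthma". The same section then states that these listed items are the independent variables of the logistic model. The abstract and section 9.7 repeat the set. Section 9.7.1 adds matching on sex, 5-year age band and years since COPD diagnosis, but on no comorbidity.

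The criterion for successful matching, also in 9.7.1.1, is a "standardized difference (detailed below) of a covariate that is less than 0.1 between treatment groups". Covariates above that limit are adjusted for afterwards, and this commitment is confined to variables in the propensity score. Sections 9.7 and 9.7.2 repeat the restriction.

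Section 9.12 describes the score differently: "The PS will be computed on the basis of a wide range of covariates related to sociodemographic characteristics, history of exacerbation, other comorbidities". The sentence goes on to include prior or concomitant use of other drugs. No drug-use term appears in the 9.7.1.1 list, and no comorbidity beyond the index and asthma.

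**The concern.** A comorbidity index adds up diseases that may differ widely in how strongly they predict pneumonia, death or health care use. If it enters the model as one score, two patients with the same value are interchangeable for matching, even if one has heart failure and the other diabetes. Should prescribers weigh such diseases differently when choosing between LAMA and ICS/LABA, the arms can come out balanced on the index and unbalanced on the diseases inside it.

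The stated safeguard need not catch this. A component disease that is not itself a variable in the score triggers no committed adjustment, however unbalanced it is. The imbalance would then pass into the hazard ratios for the primary and secondary outcomes. A larger sample would not reduce it. A reader relying on 9.12 would meanwhile believe that the score covers more than 9.7.1.1 specifies.

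**Working it through.** The plan gives no figure on this point, so there is nothing to reproduce. The check has two parts.

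**1. The sections side by side**

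| Question | 9.7 and 9.7.1.1 | 9.12 |
|---|---|---|
| Individual comorbidities in the score | Asthma only | Other comorbidities, none named |
| Summary comorbidity term | Charlson index, coding not stated | Not mentioned |
| Use of other drugs | Not listed | Included |
| Component-level balance check | Not specified | Not specified |

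The two descriptions do not agree. The list in 9.7.1.1 is the operative one, because the model specification refers back to it.

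**2. How large a hidden imbalance could be**

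The prevalences, disease rate ratios and weights below are assumptions; none comes from the documents.

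Formulas:
- Standardized difference of a binary covariate: (p1 − p0) / √{[p1(1 − p1) + p0(1 − p0)] / 2}.
- Spurious rate ratio from one disease when the drugs do not differ: [1 + p1(RR − 1)] / [1 + p0(RR − 1)].
- For two diseases taken as independent and acting multiplicatively, the product of the two ratios.

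*Illustration A: mortality.* Heart failure has rate ratio 2.5 and diabetes 1.2. They carry equal weight in the index, and the rest of the index is balanced.

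- Scenario 1: heart failure 12% v 8%, diabetes 16% v 20%. Contribution to the mean index: 0.12 + 0.16 = 0.08 + 0.20 = 0.28, so the means are equal. Spurious ratio: (1.18 / 1.12) × (1.032 / 1.04) = 1.045. Absolute standardized differences: heart failure 0.13, diabetes 0.10 (0.104 before rounding).
- Scenario 2: heart failure 15% v 8%, diabetes 13% v 20%. Both sums are again 0.28. Spurious ratio: (1.225 / 1.12) × (1.026 / 1.04) = 1.079. Absolute standardized differences: 0.22 and 0.19.

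In both scenarios each disease exceeds the plan's 0.1 limit, while the index shows a mean difference of zero. Exchanging the arms gives 1/1.045 = 0.96 and 1/1.079 = 0.93, so the direction is open.

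*Illustration B: a wider range.* Two mutually exclusive diseases of equal weight have a combined prevalence of 40% in each arm, so the distribution of the index is identical. Only one of them affects the outcome.

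| Prevalence of the prognostic disease | Its standardized difference | Spurious ratio, disease RR 1.5 to 3.0 |
|---|---|---|
| 22% v 18% | 0.10 | 1.02 to 1.06 |
| 25% v 15% | 0.25 | 1.05 to 1.15 |
| 30% v 10% | 0.52 | 1.10 to 1.33 |

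**Detectability.** With 5,000 per arm (section 9.5), the standard error of a standardized difference is about √(2/5000) = 0.02. Imbalances near or above 0.1 would be plain if the component diseases were tabulated.

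**The case against.** A reader might infer that comorbidity enters only as the Charlson total. The text does not go that far. Asthma is a separate term, and lung cancer, IPF, ILD and lung transplantation at COPD diagnosis are handled by exclusion (section 9.2). The coding of the index is never stated, and section 9.3 leaves detailed variable definitions to the SAP. A total is the natural reading, but a single linear term is not prescribed.

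A reader might also infer that the balance check cannot reveal differences in component diseases. That is too strong as well. Section 9.7 applies standardized differences to baseline characteristics without itemising them or limiting them to the score. Section 9.7.1.1 permits further adjustment and section 9.7.2 further model variables. Component-level checking is therefore unspecified, not ruled out.

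The illustrations are constructed. The zero difference on the index is built in by equal weights and exact offsetting. Illustration A concerns mortality, a secondary outcome, and nothing in the documents suggests that the arms differ in this way. Section 9.9.4 already acknowledges residual confounding. Text after 9.7.2 is blacked out, and the checklist places sensitivity analyses in 9.7.3; whether that text bears on this point cannot be judged.

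These limits stand, and they make the point an under-specification of low severity. They do not remove it. The permitted extra adjustments commit to nothing specific, and the committed rule still stops at variables in the score. By giving asthma its own term, the protocol itself accepts that one disease can matter beyond an aggregate.

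**Conclusion.** The point holds as a modest, inexpensive improvement. The operative list names no individual comorbidity apart from asthma (and exacerbation history) and otherwise rests on the Charlson index. Section 9.12 claims more than that list contains. Balance on the index does not ensure balance on its components, no component-level check is committed, and post-matching adjustment is limited to variables in the score.

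The size of any resulting bias cannot be derived from the documents. The range 1.05 to 1.08 for mortality is illustrative only: it needs the assumed prevalences and rate ratios, equal index weights and exact offsetting. Other assumed inputs run from 1.02, which is negligible, to 1.33, which is material. No figure specific to pneumonia has been worked out. The documents do not support a statement that the hazard ratios will be biased, or in which direction.

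**What to change.** In section 9.7.1.1, replace the single index item with the Charlson component diseases as separate terms, pooling rare ones, and carry the change into 9.7 and the abstract. Keep the index as a descriptive baseline row and state how it is coded. Report the standardized difference of every component after matching, and apply the existing adjustment rule for values above 0.1 to each. Reconcile 9.12 with 9.7.1.1, so that both name the same comorbidities and say whether use of other drugs is in the score.

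The cost is about 15 to 20 more terms in a logistic model on at least 10,000 patients, built from ICD-10 main and sub disease codes that section 9.6 already lists. A finer model may yield slightly fewer matched pairs within the 0.2 SD caliper; that loss has not been quantified. If it proved unwelcome, a smaller step would keep the index in the model and add the components only to the balance table and the adjustment rule, which leaves the matched set unchanged.

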9.3.3 Covariates

Age, sex and history of COPD exacerbation, income status(quartile) or medical health insurance are all matching factors and will thus inherently be accounted for.

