9.5 STUDY SIZE

In 2008~2013 NHI database, approximately 200,000 patients per year with COPD were diagnosed using COPD diagnostic code and a prescription for COPD medications (LAMA, LABA, ICS + LABA, SAMA, SABA, SAMA + SABA, PDE-4, systemic beta agonist, theophylline). In COPD patients, the use of LAMA and ICS/LABA was 26 to 37%, respectively. We expect the study to include a minimum of 5,000 patients per arm, a conservative estimate.

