9.7.2 Main analysis

For the primary effectiveness outcomes incidence rates (events per 1,000patients-years) with corresponding 95% confidence intervals (CI) will be calculated. This will be evaluated by a matched Cox proportional hazards regression model for counting processes, which allow the follow-up time to be divided into several periods and therefore control for baseline and time-dependent covariates, using the full observational period of available data, i.e. up to 11 years of follow up. The Cox proportional hazards regression will take into account the fact that individual matching (1:1) will be performed by considering the exposed patient and his/her matched controls as one stratum and including this as a stratum in the Cox proportional hazards model. Additional variables will be included in the model if available. The cumulative incidence plots will be accompanied by number of patients at risk at different time points during follow-up. For (possibly) repeating events (such as exacerbation event) additionally a Poisson regression model will be fitted for the number of events (taking into account the matching). Time in the study will be included as an offset variable in the model. The cox and Poisson models will be adjusted for unbalanced PS-variables at baseline.

The outcome will be analyzed separately for each:

- 1) Primary outcome
 - Comparison of pneumonia incidence in COPD patients using LAMA and ICS/LABA
 - Comparison of exacerbations frequency and rate in COPD patients using LAMA and ICS/LABA : moderate or severe exacerbation

Proprietary confidential information © 2022 Boehringer Ingelheim International GmbH or one or more of its affiliated companies

[figure not shown]
- Comparison of time to start triple combination therapy (time from initial 'LAMA mono' or ICS+LABA' to 'LAMA+LABA+ICS' combination) in COPD patients using LAMA and ICS/LABA

2) Secondary outcome

- Comparison of all-cause mortality differences in COPD patients using LAMA and ICS/LABA
- Comparison of lung cancer incidence in COPD patients using LAMA and ICS/LABA
- Comparison of health care utilization: Medical cost / No. of prescriptions, visits and hospitalizations (hospitalization mainly due to severe exacerbation of COPD)

Health care utilization

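### The outcome models are guaranteed to adjust for a propensity-score variable only if its matched standardized difference exceeds 0.1, so a smaller imbalance in a strong predictor such as exacerbation history may stay in the main estimates

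*Combined protocol and SAP*

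**What the plan says.** Section 9.7.1.1 judges the matching by standardized differences and ties covariate adjustment to the result: "PS-variables with standardized difference >0.1 will be adjusted for in the analyses". Below the threshold, "A standardized difference of a covariate of less than 0.1 between treatment groups in this study indicates a negligible difference". Section 9.7.2 carries the rule into the outcome models: "The cox and Poisson models will be adjusted for unbalanced PS-variables at baseline". Section 9.7 says the same.

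Two further clauses leave room for more adjustment. Section 9.7.1.1 adds that "Further adjustments can also be made as appropriate in additional models". Section 9.7.2 says of the Cox model that "Additional variables will be included in the model if available". Neither names a variable.

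Exacerbation history appears in two places. Section 9.7.1.1 lists it as an element of the propensity score, with age and sex, socioeconomic status, Charlson Comorbidity Index and asthma. Section 9.3.3 goes further: "Age, sex and history of COPD exacerbation, income status(quartile) or medical health insurance are all matching factors and will thus inherently be accounted for". Section 9.7.1, which sets out the matching, lists only sex, 5-year age band, years since COPD diagnosis and the propensity score.

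**The concern.** A standardized difference measures how far apart the arms are on a covariate. It does not measure how much that gap matters for the outcome. A gap of 0.1 does little harm in a weak predictor and more in a strong one, yet the rule treats both alike.

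Matching on the score does not make pairs alike on each component. Two patients can have the same score while only one has had an exacerbation. Components are balanced on average across the matched groups, with some remainder. If the remainder for exacerbation history is below 0.1, nothing in the plan guarantees that the main models correct for it, although the variable has already been extracted.

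The covariate set also depends on the balance result. Section 9.7.1.1 repeats the matching in each subgroup, so main and subgroup models may adjust for different variables. Exacerbation frequency is one of the primary outcomes, and there the tolerated bias can be material against the confidence interval.

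**Working it through.** **Inputs from the documents.** Adjustment trigger: standardized difference above 0.1 (9.7.1.1). Ratio: "PS matching will be done in a 1:1 ratio using the nearest-neighbor algorithm". Size: "We expect the study to include a minimum of 5,000 patients per arm, a conservative estimate". Intervals: 95%, taken as two-sided (z = 1.96).

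**No figure to reproduce.** Section 9.5 gives about 200,000 patients per year and 26% to 37% use of the two treatments. That is 200,000 × 0.26 = 52,000 and 200,000 × 0.37 = 74,000 users per year, so 5,000 per arm is a feasibility floor and not a power calculation. The documents state no event rate, covariate prevalence, covariate effect or expected interval width.

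**Assumptions, with ranges.** Proportion p with prior exacerbation: 0.30 (0.20-0.40). Relative rate R of exacerbation in those patients: 3 (2-4). Mean 0.5 events per patient over one year. Dispersion k = 1 (variance = mean + k × mean²).

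**Step 1: gap at the limit.** Difference in prevalence = 0.1 × √(p(1−p)) = 0.1 × √(0.3 × 0.7) = 0.0458. Centred on 0.30, the arms have 0.3229 and 0.2771.

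**Step 2: bias in the unadjusted rate ratio.** Factor = [1 + p₁(R−1)] / [1 + p₀(R−1)] = (1 + 0.3229 × 2) / (1 + 0.2771 × 2) = 1.6458 / 1.5542 = 1.059, or 0.057 on the log scale.

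Ends of the range:
- p = 0.20, R = 2: 1.22 / 1.18 = 1.034 (log 0.033)
- p = 0.20, R = 4: 1.66 / 1.54 = 1.078 (log 0.075)

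**Step 3: random error.** SE = √[2 × (1/(5,000 × 0.5) + 1/5,000)] = √0.0012 = 0.0346. Half-width = 1.96 × 0.0346 = 0.068 on the log scale, about 7%.

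**Step 4: ratio of bias to half-width.** Base case 0.057 / 0.068 = 0.84. Range 0.033 / 0.068 = 0.49 to 0.075 / 0.068 = 1.1.

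**Step 5: simulation.** 5,000 per arm, 30% with history, true rate ratio 1, Poisson model with robust standard errors, pairs not stratified, 300 runs per row:

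| Outcome type | R | Events per patient | Std. difference | Bias / half-width | Coverage unadjusted | Coverage adjusted |
|---|---|---|---|---|---|---|
| Frequent, overdispersed | 2 | 0.39 | 0.1 | 0.46 | 86% | 94% |
| Frequent, overdispersed | 3 | 0.48 | 0.1 | 0.79 | 66% | 96% |
| Frequent, overdispersed | 3 | 0.96 | 0.1 | 0.91 | 57% | 95% |
| Frequent, no overdispersion | 3 | 0.96 | 0.1 | 1.23 | 31% | 95% |
| Frequent, overdispersed | 3 | 0.96 | 0.03 | 0.29 | 91% | 95% |
| Rare (such as pneumonia) | 2 | 0.052 | 0.1 | 0.20 | 94% | 96% |
| Rare (such as pneumonia) | 3 | 0.064 | 0.1 | 0.36 | 89% | 95% |

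The fourth row exceeds the Step 4 range because it drops overdispersion and nearly doubles the event rate. In every row, adjusting for history brought the log-scale bias to about 0.002 or less and did not widen the interval (second row: half-width 0.0757 to 0.0725).

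**Step 6: what matching is likely to leave.** Simulated 1:1 nearest-neighbour matching with the planned caliper (30% with history, odds ratio 2 or 3 for receiving ICS/LABA) started from standardized differences of about 0.29-0.47 and left about 0.00-0.03. When matching was on the score alone, about 23-32% of pairs still differed on history. That share depends on the assumed score model and falls when history dominates the score. At 0.02, the base case gives a log bias of 0.0115, and 0.0115 / 0.068 = 0.17 of the half-width.

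**The case against.** The strongest reply is that this is a coherent plan with a stated balance criterion. Exacerbation history is in the score, and realistic matching leaves far less than 0.1. The choice of covariates looks only at baseline balance, so it cannot be steered by outcomes. The text allows more adjustment, and section 9.7 defers detail to an SAP. All of this stands, and it is why the figure at the 0.1 limit is an upper bound. It does not remove the gap: the extra clauses name nothing, one is confined to additional models, and the other sits uneasily beside the unbalanced-only rule in the same section.

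Some stronger readings are tempting, but the documents do not support them.

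- **Strong predictors go uncontrolled.** They do not. They enter the score, and only the imbalance left after matching is at issue.
- **No covariate can enter unless it fails the balance check.** The two further clauses permit it, without specifying it.
- **Years since diagnosis is ignored.** Section 9.7.1 matches on it directly, and section 9.7.2 makes each pair a stratum of the Cox model.
- **Prior exacerbation is the main driver of ICS use.** No section says so, and section 7 describes ICS as prescribed regardless of exacerbation risk. The point needs only that the plan itself treats exacerbation history as a confounder.
- **The plan accepts a bias as large as the interval half-width in general.** That requires a difference at the limit, a strong predictor and a frequent outcome. The pair-stratified Cox model would also have wider intervals, and so a smaller ratio.

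**Conclusion.** The point holds in limited form. The only specified trigger for adjusting the outcome models is a standardized difference above 0.1. No score variable is sure of a place in them otherwise, and section 9.3.3 claims more for the matching than section 9.7.1 delivers on exacerbation history.

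At the limit, and under the assumptions above, the exacerbation rate ratio could be off by 3-8%, about half to all of its 95% CI half-width. With differences of 0.02-0.03 the ratio falls to roughly 0.2-0.3. For pneumonia at about 5-6 events per 100 patients it is 0.2-0.4 even at the limit. All event rates, prevalences and covariate effects are assumed.

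The tolerance is fixed while the interval narrows as the cohort grows. At 20,000 per arm the half-width halves, so the ratio at any given difference doubles. The change is worth making because it removes avoidable residual confounding at almost no cost, not because a large bias is expected.

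**What to change.** In sections 9.7, 9.7.1.1 and 9.7.2, replace the conditional rule with a fixed covariate list:

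- The main Cox and Poisson models include the propensity-score variables not exactly matched within pairs, whatever their standardized differences: history of COPD exacerbation, Charlson Comorbidity Index, asthma, socioeconomic status, and age within the 5-year band where available. (Section 9.6 lists age and date of birth, while Annex 3 lists only an age group.)
- The Poisson model also includes sex and years since COPD diagnosis. In the pair-stratified Cox model these are already controlled where exactly matched, and they drop out because they do not vary within a pair.
- The 0.1 threshold stays as a balance diagnostic.
- The unadjusted matched estimate is reported as supportive.

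Use the same list after re-matching in subgroups, and align section 9.3.3 with section 9.7.1 on which factors are matched directly. The cost is a few sentences and a few degrees of freedom among at least 10,000 patients. The variables are already needed for the score and the matching.
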